7.7.3 Visual Analogue Scale for Craving

The VAS craving will be completed by the subject himself/herself. The first assessment will be done prior to T0 of each fixed puffing regimen and *ad libitum* use on Days -1 to 4. All other assessments will be done after T0, at 4 minutes \pm 2 minutes, at 10 minutes \pm 2 minutes, at 15 minutes \pm 2 minutes, 30 minutes \pm 5 minutes, 1 hour, 2 hours, 4 hours on each of Day -1 to Day 4.

The questionnaire will be reviewed for completeness by the study site study collaborator and subjects will be requested to complete any missing information.

7.7.4 Cough Assessment

Subjects will be asked if they have experienced a need to cough within 30 minutes after P4M3-1.7% product test at Admission (Day -2) and within 30 minutes after each fixed puffing regimen and *ad libitum* use on Days -1 to 4, and at discharge or at early termination. If the answer is 'yes', they

will be asked to complete a cough assessment questionnaire (which includes a VAS, three Likert scales, and an open question).

The VAS will assess how bothersome cough is to the subject ranging from 'not bothering me at all' to 'extremely bothersome'.

Furthermore, subjects will be asked to assess the intensity and frequency of cough and the amount of sputum production on Likert scales:

- The intensity of cough will be assessed on a 5-point Likert scale ranging from 1 to 5:
1 = very mild; 2 = mild; 3 = moderate; 4 = severe; 5 = very severe.
- The frequency of cough will be assessed on a 5-point Likert scale ranging from 1 to 5:
1 = rarely; 2 = sometimes; 3 = fairly often; 4 = often; 5 = almost always.
- The amount of sputum production will be assessed on a 4-point Likert scale ranging from 0 to 3:
0 = no sputum; 1 = a moderate amount of sputum; 2 = a larger amount of sputum;
3 = a very large amount of sputum.

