- $cC_{\text{peak}} - cC_{\text{trough}}$ versus HPT parameters (60 minutes *ad libitum* use only)
- cC_{max} versus HPT parameters (fixed puffing regimen only)
- $cAUC_{(0-4h)}$ versus HPT parameters (fixed puffing regimen only)

6. To assess amount of e-liquid use of the P4M3 variants following the 60 minutes *ad libitum* use and the fixed puffing regimen.

Endpoint:

- Weight difference of cartridge before and after each product use regimen

7. To monitor the safety and tolerability during the study.

Endpoints:

- Incidence of AEs and SAEs
- Frequency of AEs and SAEs

-
- Incidence of P4M3 device events including malfunction/misuse
 - Physical examination changes from baseline
 - Changes from baseline of VAS, three Likert scales and the open question of Cough assessment questionnaire
 - ECG changes from baseline (heart rate, PR, QRS, QT, QTcB , QTcF intervals)
 - Vital signs changes from baseline (systolic and diastolic blood pressure, pulse rate and respiratory rate)
 - Spirometry changes from baseline (FEV₁, FEV₁ % predicted, FVC, FEV₁/FVC)
 - Changes from baseline in clinical chemistry, hematology, and urine analysis safety panel (described in [Table 2](#))
 - Concomitant medications

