4.4 Appropriateness of Measurement

All laboratory measures utilized for this study are validated and are appropriate for the study assessments.

All questionnaires to be used during the study, with the exception of the cough questionnaire, are adapted versions of validated questionnaires.

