12.6.3 Safety Endpoints

In general, all safety data will be listed and tabulated using the approach described in [Section 12.1.2](#). Safety variables collected during exposure periods will also be reported by product exposure.

AE data will serve as the primary assessment of safety. Other safety variables monitored in this study include: respiratory symptoms (cough assessment VAS and Likert scales); vital signs (systolic and diastolic blood pressure, pulse rate, respiratory rate); spirometry; ECG data; clinical chemistry, hematology, and urine analysis safety panel; physical examination.

Data and information contained in this document are considered to constitute trade secrets and confidential commercial information, and the legal protections provided to such trade secrets and confidential information are hereby claimed under the applicable provisions of US law. No part of this document may be publicly disclosed without the written consent of PMI.

All AEs will be summarized by nicotine concentration (fixed puffing and *ad libitum* use combined) and overall. The number and percentage of subjects with AEs, SAEs, and device events will be tabulated by system organ class and preferred term. Summaries will also be presented for AEs leading to discontinuation, AEs leading to death, AEs by relatedness to product exposure (with and without laboratory related AEs), AEs by severity, and laboratory AEs. Tabulations will be performed for both the number of subjects experiencing an event and the number of events. Due to the laboratory schedule in this study, any lab related AEs will be assigned to P4M3 4% nicotine concentration.

Summary tables showing actual values and change from baseline of clinical findings will be provided for spirometry, ECGs, vital signs, and laboratory parameter. Descriptive statistics will be summarized by fixed puffing/*ad libitum* use and nicotine concentration and change from baseline will be presented for laboratory parameters, ECG, respiratory symptoms, and vital signs. Shift tables will be provided for laboratory and safety ECG data.

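### The sputum item in Protocol 7.7.4 has no category between none and moderate, so small amounts must be scored 0 or 1 and low-level changes from baseline are ambiguous

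*Protocol*

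**What the plan says.** Protocol 7.7.4 asks subjects whether they felt a need to cough after the Day -2 product test, after each use session on Days -1 to 4, and at discharge or early termination. Those who say yes complete a questionnaire with a VAS, three Likert scales and an open question. On sputum it states: "The amount of sputum production will be assessed on a 4-point Likert scale ranging from 0 to 3". The labels are "0 = no sputum; 1 = a moderate amount of sputum; 2 = a larger amount of sputum" and then "3 = a very large amount of sputum".

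The cough intensity scale directly above it reads "1 = very mild; 2 = mild; 3 = moderate; 4 = severe; 5 = very severe". The frequency scale starts at rarely and sometimes.

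The item feeds a listed endpoint under secondary objective 7 in Protocol 3.2: "Changes from baseline of VAS, three Likert scales and the open question of Cough assessment questionnaire". Protocol 12.6.3 has respiratory symptoms summarised descriptively, with change from baseline, by use regimen and nicotine concentration.

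On the instrument itself, Protocol 4.4 says: "All questionnaires to be used during the study, with the exception of the cough questionnaire, are adapted versions of validated questionnaires".

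**The concern.** Three of the four sputum levels are moderate or above, and the remaining one is none. The intensity and frequency items let a subject report a low-level response; the sputum item does not. A subject who brings up a little sputum has no label that fits and no instruction on which neighbouring label to take.

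At stake is how well the low end of the sputum change score can be read. The scale has only three steps, so an arbitrary choice at the lowest step can hide a real change or show one that is too large. The gap is fixed at collection: an analysis plan may collapse categories, but it cannot recover a level that subjects were never offered.

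**Working it through.** The protocol gives no figure to reproduce, and no sample-size or error-rate formula applies. The check sets the labels side by side and follows a small amount through the change score.

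**1. Labels below moderate or the middle of each scale (Protocol 7.7.4)**

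| Item | Range | Low categories offered |
|---|---|---|
| Cough intensity | 1 to 5 | very mild, mild |
| Cough frequency | 1 to 5 | rarely, sometimes |
| Sputum amount | 0 to 3 | none of this kind; 0 is absence and 1 is already moderate |

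The sputum item has four labels, and zero of them lie between absence and a moderate amount.

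**2. Effect on the change score.** Let the true state be none (N), small (S) or moderate (M). N scores 0 and M scores 1. S scores 0 or 1 according to the subject's reading.

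| True change | Recorded if S is read as 0 | Recorded if S is read as 1 |
|---|---|---|
| N to S | 0 | 1 |
| S to M | 1 | 0 |
| N to M | 1 | 1 |
| S to S, same reading both times | 0 | 0 |
| S to S, reading differs | +1 or -1 | +1 or -1 |

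Under either consistent reading, one of the two small real changes is lost and the other is recorded as a full step. If the subject varies between readings, a stable small amount can show a change of one point either way. The order of the categories is preserved throughout, and any change between levels other than S is recorded as the labels intend.

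**3. Size.** If a share p of completed questionnaires comes from subjects with a small amount, the proportion scored 1 or higher can lie anywhere from the true share at moderate or above up to that share plus p. The width of the ambiguity is p. The protocol gives no value for p, nor for the share of subjects who will cough, so p is bounded only by 0 and 1.

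**4. How often the item can be used.** One product test, plus 5 days with 2 sessions each, plus discharge: 1 + 10 + 1 = 12 occasions at most per completer, and only those at which a need to cough is reported.

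**5. Whether validation defends the wording.** Protocol 4.4 singles out the cough questionnaire as the exception among the instruments, so it offers no validated source that fixes these labels.

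**The case against.** The strongest reply is that little depends on this item. Protocol 12.6.3 says "AE data will serve as the primary assessment of safety", no hypotheses are tested (3.3), the item is completed only by subjects who report a need to cough, and variant selection rests on nicotine absorption (4.2). All of that stands and keeps the point minor. It is not a complete safeguard, though: Protocol 7.7 says symptoms captured on the questionnaires need not also be recorded as adverse events, leaving that to the investigator's discretion.

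A second reply is that subjects may treat 1 as the lowest non-zero step and ignore its label. Each subject is planned to use every variant, so a subject who always reads the labels the same way adds no spurious difference for a stable small amount. That is right, but it does not restore the lost distinction between none and small, or between small and moderate.

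A reader might also infer three stronger things, which the protocol does not support:

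- **That small amounts are the likeliest answer.** No expected sputum amount is given. Subjects are healthy, with obstructive spirometry and asthma excluded (5.1.2), so none may well be the usual answer, and the scale records it correctly.
- **That small amounts cannot be recorded at all.** The open question is part of the same questionnaire and endpoint and might capture them. Its wording is not shown, and free text would not correct the ordinal score.
- **That the endpoint as a whole is misclassified by some stated number of points.** Only small-amount answers are affected, and any percentage would rest on assumed shares of coughing subjects and of small amounts.

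**Conclusion.** The gap is real and can be read directly from Protocol 7.7.4: a small amount of sputum has to be scored as none or as moderate, and low-level changes from baseline on this item are ambiguous. The conclusion rests only on the printed labels and on the absence from 7.7.4 of a scoring rule for small amounts; it needs no assumption about how common they are. The size is unknown, because it depends on the share of small-amount answers. The consequence is limited to the low end of one Likert item in a supportive, descriptive safety endpoint, with no effect on the primary endpoints or the sample size. This is a worthwhile minor improvement, not a flaw in the trial's main conclusions.

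**What to change.** Before the first subject enters, relabel the sputum item in Protocol 7.7.4 and on the form so that the levels cover the range, for example 0 = none, 1 = small, 2 = moderate, 3 = large amount. The number of levels and the coding from 0 to 3 stay the same. The cost is a change to the labels of one item; a small downside is that scores would not be directly comparable with any other use of the present labels.

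If the form cannot be changed, tabulate the categories with the wording that subjects actually saw, and add a note that small amounts may fall in 0 or 1. Subjects should not be told to choose the moderate label for any sputum: they would be endorsing a description that they may think false.

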8 ADVERSE EVENTS

8.1 Definitions

8.1.1 Adverse Events

An AE is defined as any health – related event which is adverse or unfavorable and which either starts after ICF signature or represents a worsening of a health – related condition that existed at the time of that signature. Careful medical judgment is required to establish whether a clinical finding (including an abnormal laboratory result) is a true AE or just a manifestation of a preexisting health – related condition. An AE may or may not have a causal relationship with the study procedures or with the use of IPs.

8.1.2 Serious Adverse Events

A SAE is defined as an AE that:

- Results in death.
- Is life-threatening.
- Requires inpatient hospitalization or prolongation of existing hospitalization.
- Results in persistent or significant disability/incapacity, or
- Is a congenital anomaly/birth defect.

Important medical events that may not result in death, be life-threatening, or require hospitalization may be considered an SAE when, based on appropriate medical judgment, they may jeopardize the subject or the subject may require medical or surgical intervention to prevent one of the outcomes listed in the above definitions.

"Life-threatening" means that the subject was at immediate risk of death from the event. It might have caused death if it had occurred in a more serious form.

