4.5 Study Stopping Criteria

The study may be stopped if the subjects are placed at risk because of clinically significant findings or SAEs that, e.g.:

- are assessed as causally related to P4M3.
- are not considered to be consistent with continuation of the study
- are not consistent with the information provided in Section 6.5 of the current IB

The Sponsor, Investigator, and/or IRB reserve the right to terminate or suspend the study at any time; however this should be discussed between the relevant parties beforehand and the reason for such decision recorded. Should this occur, all data available will also be recorded in the case report forms (CRFs). The Investigator should notify the IRB in writing of the study's completion or early discontinuation.

In the event that the study is terminated early, every effort should be made by the Investigator, investigational site personnel, and Sponsor to follow AEs and SAEs for all subjects until the end of the passive safety FU.

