**Table 3. Expected AEs: Foreseeable Risks with Subjects' Own e-Cigarette Use**

Risks Associated with:	Potential Adverse Events
Over-exposure to nicotine / nicotine acute intoxication / poisoning	Mild intoxication : Nausea, hyper-salivation, abdominal pain, vomiting, diarrhea, cold sweat, diaphoresis, headache, dizziness, hearing and visual disturbances, mental confusion, agitation, tremor, weakness, weak analgesia, increase of respiratory reflex and coughing, increase bronchial secretions, shortness of breath (as a consequence of stimulation of lung mechanoreceptors), increase in heart rate and blood pressure
Under-exposure to nicotine / tobacco and nicotine withdrawal symptoms	Affective symptoms : Irritability/anger/frustration, anxiety/anxious/nervous, depressed mood /depression/ sad/anhedonia, insomnia/sleep problems, dysphoria, hyperalgesia, impatient, restlessness, nightmares/ dreaming Somatic symptoms : tremors, bradycardia, gastrointestinal discomfort, nausea, constipation, increased appetite, hungry, weight gain, coughing, dizziness, sore throat, mouth ulcer Cognitive symptoms : difficulty concentrating, impaired memory
Hypersensitivity reactions	Susceptible consumers may experience hypersensitivity reactions such as skin disorders (e.g., localized or generalized rash, pruritus), urticaria and/or angioedema

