8.3 Reporting and Follow-Up of Serious Adverse Events

Any SAE observed during the period of collection by any of the parties involved in this study (including the Investigational site personnel) must be reported by that party within 24 hours of first awareness to UBC Pharmacovigilance, as described in the safety management plan (SMP).

SAEs considered related to the IP and observed by, or reported to, any of the parties involved in this study (including the Investigational site personnel) after the period of collection must also be reported by that party within 24 hours of first awareness to UBC Pharmacovigilance for safety surveillance purposes.

All the SAE report forms must be either faxed or sent as an attachment to an e-mail message to UBC Pharmacovigilance:

UBC Pharmacovigilance:	Fax number:	██████████
	E-mail:	██████████
	Address:	United BioSource Corporation UBC Pharmacovigilance [name] [name] Switzerland

As further information regarding an already reported SAE becomes known to any of the parties involved in this study, such follow-up information must be reported on a new SAE report form, marked as a follow-up report and submitted to UBC Pharmacovigilance according to the same timelines described above. The follow-up SAE report form must include the minimum information required for completion and only changed/new information needs to be specified. Information provided in the follow-up SAE report form generally supersedes any information that was initially reported.

The SAE report form to be used in this study is provided as a separate document. All SAEs will also be recorded on the relevant CRF page, in addition to the SAE report form.

The Investigator or designee is responsible for submitting the relevant reports of SAEs that occur during the study to the local IRB), according to local regulations and in line with the respective safety management plan.

If applicable, SAEs will be reported by Sponsor to the Center for Tobacco Products Office of Science within 15 days after the report is received by the Sponsor.

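### Section 8.1.2 defines "Is life-threatening" by actual immediate risk and then by a hypothetical worse event, so an event with no immediate risk of death could be classed as an SAE

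*Protocol*

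**What the plan says.** Protocol section 8.1.2 lists the seriousness criteria. One of them, with no further condition attached, is "Is life-threatening". The closing lines of the section define the term in two consecutive sentences:

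- The first sentence says that the term "means that the subject was at immediate risk of death from the event".
- The second sentence then says of the same event, affirmatively: "It might have caused death if it had occurred in a more serious form".

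Between the list and this definition stands a separate route to seriousness: "Important medical events that may not result in death, be life-threatening, or require hospitalization may be considered an SAE when" medical judgment finds that the subject may be jeopardized or may need intervention to prevent a listed outcome.

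Three other parts of the protocol depend on whether an event is serious:

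- Section 3.2, secondary objective 7, has as an endpoint "Incidence of AEs and SAEs".
- Section 8.3 requires that an SAE seen during the collection period "must be reported by that party within 24 hours of first awareness to UBC Pharmacovigilance".
- Section 8.2.6 ends follow-up of ongoing non-serious events when the passive safety period closes, but continues follow-up of SAEs until they resolve, stabilize or are explained.

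No other section defines the term or corrects the second sentence.

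**The concern.** The two sentences ask different questions. The first asks what the event did to the subject. The second asks what a more severe version of it might have done. Its conditional wording implies that the event as it occurred was not of that severity. The sentence is affirmative, sits inside the definition, and nothing marks it as an exclusion.

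An investigator who takes the second sentence at its word could class as serious an event that posed no immediate risk of death. A colleague who stops at the first sentence would not. The same event would then be counted, reported and followed differently according to which sentence was applied. In a study this small, a safety endpoint should not depend on that choice.

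**Working it through.** No arithmetic applies: the point uses no rate, sample size or error level, and the protocol states no figure to reproduce. The check is whether any reading of the two sentences gives one clear test that needs both of them.

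**Inputs, all from section 8.1.2.**

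- *A*: the subject was at immediate risk of death from the event as it occurred (first sentence).
- *B*: the event might have been fatal in a more serious form (second sentence).

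**Relation between them.** An event that already put the subject at immediate risk of death might certainly have killed in a worse form, so A implies B. The reverse fails: B can hold where there was no immediate risk. The readings can therefore differ only for events where B holds and A does not.

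| Reading of the second sentence | Resulting test | Event with B but not A | Effect |
|---|---|---|---|
| Further condition (A and B) | A | Not life-threatening | Sentence is redundant |
| Explanation of the first sentence | B | Life-threatening, so an SAE | Definition is widened |
| Alternative (A or B) | B | Life-threatening, so an SAE | Definition is widened |
| Exclusion of the hypothetical | A | Not life-threatening | Sentence clarifies, but is not written this way |

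Only the last reading gives the sentence a useful job, and it is the one the wording does not support.

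**Is the hypothetical needed as a safety net?** No. The important-medical-events paragraph of section 8.1.2 already admits events that are not life-threatening but may jeopardize the subject, subject to medical judgment. Read literally, the second sentence would bypass that judgment.

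**What follows for an event with B but not A.**

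| | First sentence only | Second sentence applied |
|---|---|---|
| SAE endpoint (section 3.2) | Not counted | Counted |
| 24-hour report (section 8.3) | Not required | Required |
| Follow-up after the 7-day period (section 8.2.6) | Ends | Continues until resolved, stabilized or explained |

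**Direction.** Because A implies B, every event that meets the immediate-risk test qualifies under all four readings. A misreading can add SAEs but cannot remove one.

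**The case against.** The best defence is that the first sentence carries the definition. It says what the term means, and the second sentence begins with a pronoun that can refer back to the event just defined. There is no word such as *or* to open a second route. Read that way, both conditions apply and no event is added. This is a fair reading, and it is why the finding is that the wording could widen the definition, not that it must. It does not rescue the text. On that reading the second sentence is idle, and nothing tells the investigator to prefer it.

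It is also fair that the error is on the cautious side, that no serious event would be missed, and that intensity is graded separately in section 8.2.3, so a mild event would still be recorded as mild. These points limit the harm. They do not make the classification consistent.

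Several stronger conclusions are tempting, and the protocol does not support them:

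- **That many events would become serious.** No adverse event rates are given, and the number affected may be small.
- **That Table 3 shows how many event types are affected.** It lists symptoms of mild intoxication under the heading "Over-exposure to nicotine / nicotine acute intoxication / poisoning". But the table covers subjects' own e-cigarettes, while section 8.2.5 refers P4M3 to the Investigator's Brochure. It also does not say which listed events have a fatal form.
- **That one reclassified event is 1/16 = 6.25% incidence.** Sixteen is the number to be randomized. Section 12.3.3 counts everyone exposed to P4M3, including at the admission product test, and the synopsis counts all enrolled subjects. Subjects who leave after that test may be replaced, so the denominator can exceed 16.
- **That the study stopping criteria would be met.** Section 4.5 says "The study may be stopped if the subjects are placed at risk because of clinically significant findings or SAEs that, e.g" and then gives examples. It is discretionary and requires that subjects be at risk. A label of serious does not by itself meet it.
- **That a *not* was dropped in drafting.** This is plausible, but it is an inference. The protocol holds no other version of the sentence, and the finding does not depend on it.

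**Conclusion.** The definition is wrong as written, and the point is minor. Section 8.1.2 pairs a test of actual immediate risk with an affirmative test of a hypothetical worse event. The second is either redundant or widens the SAE criterion, and the text does not settle which.

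The consequence is possible inconsistency between investigators in the SAE endpoint, in 24-hour reporting and in follow-up beyond 7 days. The likely direction is over-reporting. Its size cannot be estimated from the protocol.

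The conclusion rests on two things: that an event with immediate risk of death always satisfies the hypothetical test, and that no guidance outside the protocol already tells the site how to read the sentence. The SAE report form is a separate document and was not available.

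**What to change.** Reconcile the two sentences so that only the immediate-risk test applies. Either of these would do:

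- delete the second sentence; or
- rewrite it as an explicit exclusion, for example: *It does not include an event that might have caused death had it occurred in a more serious form.*

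Leave the important-medical-events paragraph unchanged, since it keeps the judgment-based route for events that are not life-threatening but may jeopardize the subject. Check whether the SAE report form or its guidance repeats the definition and, if so, align it.

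The cost is one sentence in section 8.1.2, plus matching text on the form if it appears there. No assessment, schedule, sample size or analysis changes.
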